Patients with end-stage liver disease (ESLD) have poor physical fitness and muscle wasting (sarcopenia). Both conditions have been associated with elevated mortality before and after liver transplantation (LT). Limited data have shown that exercise benefits patients with chronic liver disease/cirrhosis, however, there are no studies with ESLD patients potentially eligible for LT. Effectively improving physical fitness and sarcopenia in ESLD should positively impact clinical outcomes before/after LT. The primary aim of this study is to improve both physical fitness and sarcopenia in ESLD patients through a 12-week physical training program. Secondary aims will focus on changes in anthropometrics, body composition, quality of life, and metabolic profile. This is a randomized clinical trial including 50 patients, with half allocated to the active group (physical training program) and half to standard of care. Physical training program will consist on achieving $\geq 10,000$ steps/day with an increase of ≥ 4000 above the baseline, facilitated by the feedback from daily step counts and behavioral modification therapy (favoring change towards a more active lifestyle). All participants will have to wear a pedometer bracelet (Fitbit) throughout duration of study (reads blinded to controls), and will receive a daily essential amino acid (EAA) supplement containing approximately 2.25 g of L-leucine along with nutritional consultation. Cardiorespiratory exercise test (CRET), 6-minute walk test (6MWT), and abdominal CT scan will be performed in all participants before and after the period of study to assess for physical fitness and sarcopenia. Anthropometrics, bioelectrical impedance, whole-body DEXA scan, sickness impact profile questionnaire, and the metabolic profile will be obtained at baseline and after completion of the study as well. Blood EAA levels, myostatin, and insulin-related growth factor-1 will be determined at baseline, and at week 12 of study. Durability of changes 6 months post-LT will be assessed as well, when applicable.

INTRODUCTION

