provocative study has shown that LT by itself is not capable of improving cardiorespiratory endurance, as shown in the lack of significant improvement in $VO_{2\text{max}}$ in 20 patients who had it tested before and more than 1 year after LT. The mild increase in $VO_{2\text{max}}$ from 63% to 71% - and 25% of patients showing decreased $VO_{2\text{max}}$ - mostly correlated with the improvement in hemoglobin, and stopping of the beta-blocker. Although there was likely some improvement in skeletal muscle physiology, as suggested by changes in peak lactate concentration, LT had no major impact in aerobic capacity and cardiorespiratory endurance.(19) This suggests that, even though poor physical fitness and sarcopenia are primarily driven by ESLD, restoration of normal liver function by means of LT is not enough to positively impact physical fitness. Likely in relation to the lack of changes in lifestyle favoring healthy habits, patients progressively gain weight after liver transplantation,(20) and it is not surprising to find a high prevalence of the metabolic syndrome (>50% after the first year post-LT; >50% of what is observed in the general population), particularly hypertension and diabetes mellitus (>60% after first year post-LT), and are at great risk for cardiovascular complications.(21)

Although there are some conflicting data regarding what benefits physical activity or exercise confers to various morbid states, it is in general conceived that improving physical fitness is beneficial, both by preventing deterioration of a state of health, and by helping diseased conditions through adaptation.(22, 23) In chronic liver disease, and particularly in the setting of ESLD, there is a great paucity of data regarding the beneficial effects that exercise or a physical activity program can offer to patients. Actually, to date, there is no robust evidence from large randomized trials to sustain that the deterioration in physical fitness and sarcopenia that patients with ESLD are exposed to, is reversible by any type of intervention.

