 - It is expected to find improved anthropometrics, decreased fatty mass, and increased fat-free mass in the active arm, when compared to the control arm.
- The changes in quality of life at the end of the study for each group.
 - It is expected to find improvements in quality of life in the active arm, when compared to the control arm.
- Safety of the physical training program, by systematically documenting episodes of variceal bleeding, and hepatic encephalopathy.
 - No increased risk for complications such as GI bleeding and encephalopathy is expected for the active arm with current research design.
- The changes in the metabolic profile (fasting glucose, fasting insulin, lipid profile (total cholesterol, LDL-cholesterol, HDL-cholesterol, triglycerides) at the end of the study for each group.
 - It is expected to have an improved metabolic profile in the active arm, when compared to the control arm.
- The changes in myostatin and insulin-related growth factor 1 (IGF-1) before and after 12 weeks of study.
- In patients undergoing liver transplantation, extension of training program benefits 6 months after liver transplant (reassessment of physical fitness, sarcopenia, anthropometrics, body composition, and metabolic profile).
 - Durability of the beneficial benefits of the training program will be expected across all evaluated variables, with no changes in the control arm after transplant.

RESEARCH STRATEGY

Significance

Unlike other chronic diseases (*i.e.* diabetes mellitus), there are no recommendations for physical training and exercise in patients with cirrhosis. This derives from the fact that there is a paucity of data on the physiologic effects of exercise in patients with cirrhosis and portal hypertension, as well as on the benefits that such training can bring in the long term. Moreover, some safety concerns have been raised in the past particularly with regards to an increased risk for variceal bleeding and HE. Apart from a few pilot studies using supervised exercise as an intervention there are no clinical trials addressing the benefits of an exercise program in patients with ESLD. Furthermore, no study has looked into how a training program can translate into benefits after LT, and since LT patients have a very high risk for metabolic and cardiovascular disease, such a study is highly awaited.

Innovation

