The questionnaire Sickness Impact Profile (SIP) will be used to assess changes in the quality of life. Recent evidence suggests SIP to be superior to SF-36 in detecting health-related quality of life changes occurring in patients with ESLD. Metabolic profile will include determinations of fasting glucose, insulin (in subjects without diabetes mellitus), lipid profile (triglycerides, total-cholesterol, HDL-cholesterol, LDL-cholesterol), and HbA1c. Both SIP and the metabolic profile will be repeated after completion of the study period (12 weeks). The metabolic profile will be repeated 6 months after LT as well.

Randomization

Each participant will be randomly assigned to the active (physical activity + behavioral therapy + nutritional intervention) or control (nutritional intervention) group. The random allocation sequence will be generated using computer-generated random numbers. There will be no stratification in the randomization process, and allocation will be concealed.

Statistical analysis

Subjects sample has been defined by convenience, as there is no precedent for sample estimation. Descriptive statistics will include mean \pm SD and/or median (range), according to distribution of data. Shapiro-Wilk test will be used to assess normal distribution. Results on VCO₂ will be plotted against VO₂, whereas lactate, and ammonia will be plotted against VO_{2max}, for all patients as an aggregate. The lines determining the anaerobic, lactate, and ammonia thresholds will be calculated by linear regression. Continuous variables comparisons within groups will be done with paired t-test or Wilcoxon, whereas between groups will be done with t-test or Mann-Whitney. Categoric variables will be compared with chi-square or Fisher's exact test, as appropriate. Agreement between methods used to address body composition, bioelectrical impedance and DXA, will be investigated with Bland-Altman test.

Data collection and handling

Title: A physical activity program in end-stage liver disease
PI: [name]

Apart from the data generated by the study demographics and clinical information to properly classify the hepatic functional and cardiorespiratory status of each participant will be retrieved from the electronic medical record (EMR). Such information will include results from standard of care laboratories, imaging, and other special studies (EGD, pulmonary function tests, echocardiogram), to calculate MELD score, and Child-Turcotte-Pugh scores.

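### The post-transplant durability aim is worded arm by arm with no deciding contrast, expects unchanged controls against the protocol's own background on weight and metabolic profile, and compares a subset formed after randomisation

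*Combined protocol and SAP*

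**What the plan says.** The last secondary aim under SPECIFIC AIMS reads: "In patients undergoing liver transplantation, extension of training program benefits 6 months after liver transplant". It covers physical fitness, sarcopenia, anthropometrics, body composition and metabolic profile. The expectation beneath it is that durability "will be expected across all evaluated variables, with no changes in the control arm after transplant". The abstract gives the assessment conditional status: "Durability of changes 6 months post-LT will be assessed as well, when applicable".

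The other efficacy aims that state an expectation (thresholds, anthropometrics and body composition, quality of life, metabolic profile) word it as a comparison with the control arm. The durability aim does not; it describes each arm separately.

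The Statistical analysis section gives one general rule: "Continuous variables comparisons within groups will be done with paired t-test or Wilcoxon, whereas between groups will be done with t-test or Mann-Whitney". Nothing there is specific to the post-transplant visit. It does not name the contrast that decides durability, the reference visit (baseline or week 12), or how patients who are never transplanted are handled. The sample size has no power basis: "Subjects sample has been defined by convenience, as there is no precedent for sample estimation". The trial is described as "including 50 patients, with half allocated to the active group (physical training program) and half to standard of care".

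**The concern.** Two separate weaknesses meet in this aim.

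**The reference.** The Introduction says of recipients in general that "patients progressively gain weight after liver transplantation", and reports a "high prevalence of the metabolic syndrome (>50% after the first year post-LT". Both belong to domains in which the aim expects controls to stay unchanged. If durability is read from each arm's own paired test, change due to transplant is mixed with change due to training.

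**The subset.** Only patients who reach transplant contribute, and that is settled after randomisation. The Introduction itself suggests that training may reduce loss from the waiting list, so arm could influence who is compared. Time from week 12 to transplant is also uncontrolled.

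At stake is whether a statement that benefit lasts, or does not last, after transplant reflects training, or instead transplant and who received it.

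**Working it through.** The plan states no power, effect size, SD or expected number of transplants for this aim, so there is no figure to reproduce. The check compares the text domain by domain and then illustrates the size under stated assumptions.

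**1. The expectation against the Introduction**

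| Domain | Introduction on recipients after transplant | Fits unchanged controls? |
|---|---|---|
| Weight | Progressive gain | No |
| Metabolic profile | Metabolic syndrome above 50% after the first year | No |
| VO2max | 63% to 71%, n = 20, more than 1 year after transplant; mild, not significant; 25% fell; linked mainly to haemoglobin and stopping of the beta-blocker | Largely yes |
| Muscle area | No figure | Cannot be judged |

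The VO2max and metabolic syndrome figures come from about a year or more after transplant; the trial measures at 6 months.

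**2. How often a per-arm reading of VO2max would mislead**

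Assumptions: no training effect; a mean change of 71 − 63 = 8 points in both arms; normal data; two-sided 0.05; 5 to 15 transplanted per arm (20% to 60% of 25).

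The SD of change is not given. Two values can be inferred:
- From non-significance: SD ≥ 8 × √20 / t(0.975, 19) = 17.1.
- From 25% falling: SD = 8 / z(0.75) = 11.9. This implies t = 8 / (11.9/√20) = 3.0, which does not fit non-significance, so it serves only as a low end.

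Let p be the chance of a significant gain in one arm (paired t-test, noncentral t). The chance that active is significant and control is not is p(1 − p).

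| Transplanted per arm | p, SD 11.9 | p(1 − p) | p, SD 17.1 | p(1 − p) |
|---|---|---|---|---|
| 5 | 21% | 17% | 13% | 11% |
| 10 | 48% | 25% | 26% | 19% |
| 15 | 68% | 22% | 39% | 24% |

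Since 17.1 is the smallest SD that fits non-significance, 11% is not a floor. A larger SD would pull the rate down towards 0.025 × 0.975, about 2.4%.

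**3. The between-arm test under the same conditions**

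A transplant change common to both arms cancels. In 100,000 simulated trials at each of 5, 10 and 15 per arm (SD 11.9), the two-sided false-positive rate was 4.9% to 5.0%, with about 2.5% favouring active.

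**4. Selection into transplant**

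Suppose the best-prognosis share q of each arm is transplanted, and prognosis correlates ρ with outcome. The bias in the between-arm contrast, in SD, is ρ × [φ(z_a)/q_a − φ(z_c)/q_c], where z is the normal cut-off for each share. All inputs are assumed.
- Equal shares: 0.
- 30% active, 50% control: 0.11 (ρ = 0.3) to 0.18 (ρ = 0.5).
- 20% active, 60% control: 0.23 to 0.38.

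If training instead raised the share transplanted in the active arm, swapping the shares gives the same sizes with the opposite sign.

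**5. Precision of the between-arm contrast**

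Two-sample t-test, 80% power, two-sided 0.05: detectable difference 2.02 SD at 5 per arm, 1.51 at 8, 1.32 at 10, 1.20 at 12 and 1.06 at 15. It would be 0.81 SD even if all 25 per arm were transplanted.

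**The case against.** The case against is substantial, and most of it limits the point.

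- **An expectation is not a rule.** A reader might infer that durability will be judged against an unchanged control arm. The sentence is a predicted result, as under other aims, and sets no criterion. Between-group tests are already planned, transplanted controls are reassessed too, and a shared transplant effect then cancels. This stands: the harm needs either a per-arm reading or arm-dependent selection. The remaining gap is that the plan does not rule out the per-arm reading, and the aim's wording leans towards it.
- **The background does not contradict every domain.** A reader might cite the rise from 63% to 71% as proof that untrained recipients become fitter. The Introduction concludes the opposite, that transplant did little for aerobic capacity, and it gives no muscle-area figure. The conflict is limited to weight and metabolic profile.
- **Direction.** A reader might infer that transplant changes would generally pass for a training benefit. The documented weight and metabolic changes are adverse, so within the active arm they would more often hide a lasting benefit. Mimicry is plausible mainly for VO2max, and less certain there.
- **A flat control arm is informative.** If controls truly did not change, that would argue against a transplant effect. This is correct; the error lies in taking a non-significant paired test in a handful of patients as no change.
- **Imprecision is not bias.** The 2.0 to 1.2 SD figures show only that the contrast is weak at assumed numbers.
- **Weight of the result.** A reader might infer that a later trial or policy rests on this aim. The Innovation section says that of the study's results as a whole, as preliminary evidence.

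**Conclusion.** The point holds in limited form. The durability aim has no deciding contrast and no reference visit. Its blanket expectation for controls conflicts with the Introduction on weight and metabolic profile. The comparison is confined to patients selected after randomisation, which the plan does not acknowledge.

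A per-arm reading could hide a lasting benefit on weight or metabolic profile, or, less certainly, mimic one on VO2max. For VO2max the misleading pattern arises in about 11% to 25% of trials under the assumptions shown, and less often if the SD is above 17.1. The between-arm test removes that error but not selection, whose illustrative size is 0 to 0.38 SD in either direction. Transplant numbers, alpha, SDs, shares and correlations are all assumptions.

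This is a minor-to-moderate point on a secondary aim; it does not touch the 12-week comparisons.

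**What to change.** - **SPECIFIC AIMS, last secondary aim:** replace the expectation of unchanged controls with a comparison against the control arm, as in the other efficacy aims.
- **Statistical analysis:** name the between-arm difference at 6 months after transplant, adjusted for the pre-training baseline value, as the deciding contrast, and report it with a 95% CI. State that within-arm tests will not be used to claim durability.
- **Reporting:** give numbers transplanted and time from week 12 to transplant by arm, and label the result descriptive and non-randomised.

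Baseline adjustment does not remove selection into transplant; the label and the by-arm counts let a reader judge it. With an assumed 5 to 12 transplanted per arm, only differences of about 2.0 to 1.2 SD are detectable at 80% power, so the interval should carry the message rather than a p-value.

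The cost is wording and a weaker durability claim. The outcome measurements are already planned; the transplant date for each patient is the only other item needed.
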